Fibrates and niacin are clearly effective at raising HDL-C and lowering TG concentrations; fibrates also raise LDL-C in patients with very high TGs (≥ 500 mg/dL). However, their effects on vascular events remain uncertain. Several large-scale trials of fibrate therapy have been completed in the past few years. Although some of these trials have suggested benefit, others have shown no effect, leading to uncertainty about the presence and magnitude of any CV protective effects and difficulties for clinicians in interpretation of the results (Jun 2010). The ACCORD-Lipid study (Ginsberg 2010) reported no overall benefit for fenofibrate plus statin therapy over statin monotherapy, although a suggestion of benefit was observed in subjects with dyslipidemia defined by high TG and low HDL-C. Similarly, studies of niacin as add-on therapy to statin have not demonstrated a benefit with regard to CV outcomes in

their full study populations (see [AIM-HIGH](#) and [HPS2-THRIVE](#)), although benefit was observed in a subset of AIM-HIGH patients with high TG and low HDL-C. While such subgroup analyses are suggestive of benefit in certain patients with dyslipidemia, the lack of benefit in the primary study populations nonetheless raises further questions about the usefulness of these agents.

There are also safety issues with the above agents that limit their clinical use. Statins, particularly at high doses, may cause increases in hepatic transaminases and are also known to cause myopathy and occasionally rhabdomyolysis, which may lead to death from acute renal failure. This risk may be increased when fibrates and statins are co-administered and many clinicians will avoid co-prescribing these 2 medications. Fibrates are also associated with interactions with warfarin and hepatic transaminase elevations. The utility of niacin is limited by the occurrence of severe flushing and associated symptoms which can be difficult to manage even with careful dose titration and pre administration of aspirin or other non-steroidal anti-inflammatory drugs. Niacin is also associated with impairment of glucose tolerance and precipitation of attacks of gout in susceptible patients.

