10.2. AEs

An AE is defined as any untoward medical occurrence, which does not necessarily have a causal relationship with the medication under investigation. An AE can therefore be any unfavorable and/or unintended sign (including an abnormal laboratory finding), symptom, or disease temporally associated with the use of an investigational medication product, whether or not related to the investigational medication product. All AEs, including observed or volunteered problems, complaints, or symptoms, are to be recorded on the appropriate CRF. Each AE is to be evaluated for duration, intensity, and causal relationship with the study medication or other factors.

AEs, which include clinical laboratory test variables, will be monitored from the time of informed consent until study participation is complete. Patients should be instructed to report any AE that they experience to the investigator. Beginning with Visit 2, investigators should assess for AEs at each visit and record the event on the appropriate AE CRF.

Wherever possible, a specific disease or syndrome rather than individual associated signs and symptoms should be identified by the investigator and recorded on the CRF. However, if an observed or reported sign or symptom is not considered a component of a specific disease or syndrome by the investigator, it should be recorded as a separate AE on the CRF.

Any medical condition that is present when a patient is screened or present at baseline that does not deteriorate should not be reported as an AE. However, medical conditions or signs or symptoms present at baseline and that change in severity or seriousness at any time during the study should be reported as an AE.

Clinically significant abnormal laboratory findings or other abnormal assessments that are detected during the study or are present at baseline and significantly worsen will be reported as AEs or SAEs. The investigator will exercise his or her medical and scientific judgment in deciding whether an abnormal laboratory finding or other abnormal assessment is clinically significant.

The investigator will rate the severity (intensity) of each AE as mild, moderate, or severe, and will also categorize each AE as to its potential relationship to study drug using the categories of Yes or No.

Severity:

- Mild – An event that is usually transient in nature and generally not interfering with normal activities.

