- Moderate – An event that is sufficiently discomforting to interfere with normal activities.
- Severe – An event that is incapacitating with inability to work or do usual activity or inability to work or perform normal daily activity.

Causality Assessment:

The relationship of an AE to the administration of the study drug is to be assessed according to the following definitions:

- No (unrelated, not related, no relation) – The time course between the administration of study drug and the occurrence or worsening of the AE rules out a causal relationship and another cause (concomitant drugs, therapies, complications, etc.) is suspected.
- Yes (related, probably related, possibly related) – The time course between the administration of study drug and the occurrence or worsening of the AE is consistent with a causal relationship and no other cause (concomitant drugs, therapies, complications, etc.) can be identified.

The following factors should also be considered:

- The temporal sequence from study medication administration
- The event should occur after the study medication is given. The length of time from study medication exposure to event should be evaluated in the clinical context of the event.
- Underlying, concomitant, intercurrent diseases
- Each report should be evaluated in the context of the natural history and course of the disease being treated and any other disease the patient may have.
- Concomitant medication
- The other medications the patient is taking or the treatment the patient receives should be examined to determine whether any of them might be recognized to cause the event in question.
- Known response pattern for this class of study medication
- Clinical and/or preclinical data may indicate whether a particular response is likely to be a class effect.
- Exposure to physical and/or mental stresses
- The exposure to stress might induce adverse changes in the patient and provide a logical and better explanation for the event.
- The pharmacology and pharmacokinetics of the study medication
- The known pharmacologic properties (absorption, distribution, metabolism, and excretion) of the study medication should be considered.

Unexpected AEs – An unexpected AE is an AE either not previously reported or where the nature, seriousness, severity, or outcome is not consistent with the current Investigator's Brochure.

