10.3. Serious Adverse Event Reporting – Procedure for Investigators

10.3.1. Initial Reports

All SAEs occurring from the time of informed consent until 28 days following the last administration of study medication (or until 28 days following study completion for ODIS patients) must be reported to the Sponsor or designee **within 24 hours** of the knowledge of the occurrence (this refers to any AE that meets any of the aforementioned serious criteria). SAEs that the investigator considers related to study medication occurring after the 28-day follow-up period will also be reported to the Sponsor or designee.

The investigator is required to submit SAE reports to the Institutional Review Board (IRB) or Independent Ethics Committee (IEC) in accordance with local requirements. All investigators involved in studies using the same investigational medicinal product (IMP) will receive any Suspected Unexpected Serious Adverse Reaction (SUSAR) reports for onward submission to their local IRB as required. All reports sent to investigators will be blinded.

In addition, regulatory agencies will be notified of SAEs per the requirements of the specific regulatory jurisdiction regulations and laws.

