An overall summary of patients with at least one TEAE, severe TEAE, related TEAE, SAE, related SAE, TEAE leading to discontinuation of study drug, adjudicated as a clinical event, and leading to death will be presented by treatment group. Tabular summaries by SOC and preferred term will include all AEs, severe TEAEs, related TEAEs, serious TEAEs (SAEs), related SAEs, TEAEs leading to permanent study drug discontinuation, TEAEs that were adjudicated as events, and TEAEs leading to death.

For the purpose of analysis, TEAEs with a reported relatedness of related, probably related, or possibly related will be characterized as "Related". AEs assessed as "Not Related" will be classified as not related to study drug. In instances where a patient may have had multiple TEAEs with differing levels of severity or relatedness, the most severe or most related event,

respectively, will be reported for the severity and relatedness tables. For the purpose of analysis, missing AE relationship will be presented as 'related' in tables and missing in listings. In addition, tables that describe the collected data and that include a 'missing' relationship category where appropriate will be presented. Missing AE severity will be presented in a 'missing' category in tables and as missing in listings.

Pre-randomization AEs and TEAEs will be listed separately. In addition, listings will be provided of SAEs and AEs meeting criteria for adjudication (including whether the event was adjudicated as an endpoint or ruled out). Deaths will be presented in a listing that includes the AE leading to death, demographic data, details of study treatment, and relationship of the AE leading to death to the study drug.

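### The Yes and No causality definitions in protocol 10.2 leave two of four combinations without a category, and Yes contradicts its own possibly-related label

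*Combined protocol and SAP*

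**What the plan says.** Protocol 10.2 has the investigator "categorize each AE as to its potential relationship to study drug using the categories of Yes or No". There is no third answer.

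Under Causality Assessment in the same section, No applies when the time course "rules out a causal relationship and another cause (concomitant drugs, therapies, complications, etc.) is suspected". Yes applies when the time course "is consistent with a causal relationship and no other cause (concomitant drugs, therapies, complications, etc.) can be identified". The label attached to that second definition reads "Yes (related, probably related, possibly related" (closing bracket omitted). A list of further factors follows. On concomitant medication it says that the patient's other treatments "should be examined to determine whether any of them might be recognized to cause the event in question".

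SAP 4.8.1 follows the label: "TEAEs with a reported relatedness of related, probably related, or possibly related will be characterized as" related. It then uses that classification in the summaries of related TEAEs and related SAEs, and lists the relationship to study drug for events leading to death.

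On reporting, protocol 10.3.1 sends all SAEs to the sponsor until 28 days after the last dose, or 28 days after study completion for patients off drug but still in the study. Beyond that, "SAEs that the investigator considers related to study medication occurring after the 28-day follow-up period will also be reported".

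Two background facts matter. Inclusion criterion 2 (protocol 4.1) requires stable statin therapy at entry. Protocol 1.4 states: "Statins, particularly at high doses, may cause increases in hepatic transaminases".

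**The concern.** Each definition joins two conditions with *and*. A pair of such definitions covers all events only if one is the negation of the other, and here neither is. The most ordinary case in a medicated population, an event whose timing fits the study drug but which has another possible explanation, fails both.

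The gap also sets the text against itself. Possibly related normally describes an event with a competing explanation. The label puts such an event under Yes; the definition beside that label keeps it out. One investigator may follow the label and another the definition, and both can cite section 10.2. The field is mandatory, so the disagreement is resolved site by site and is invisible in the database.

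At stake are the outputs built on the rating: the related-TEAE and related-SAE tables, the relationship entry in the death listing, SAE reporting after the 28-day window, and any SUSAR decision that relies on the investigator's answer.

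**Working it through.** No figure in the plan depends on these definitions, so there is nothing to reproduce. The check is logical.

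**Step 1: cross the two conditions.** Treat timing as either ruling causality out or consistent with it, and another cause as either present (suspected or identifiable) or absent. Read each definition as written, with both parts required.

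| Timing | Another cause | Category under 10.2 |
|---|---|---|
| Rules out | Present | No |
| Rules out | Absent | none |
| Consistent | Present | none |
| Consistent | Absent | Yes |

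Two of the four cells are undefined. If timing can also be indeterminate, the gap only widens.

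**Step 2: compare definition, label and SAP for the consistent-and-present cell.** The Yes definition excludes it, because another cause can be identified. The Yes label includes it as possibly related. SAP 4.8.1 counts possibly related as related. The No definition excludes it too, because timing does not rule causality out. Two of these four statements place the event under related, and none places it under No.

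**Step 3: see whether the further factors close the gap.** They are to be considered in addition to the definitions, and they do not withdraw the condition that no other cause be identifiable. The concomitant-medication factor directs attention to alternative causes, which under the definition leads away from Yes.

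**Step 4: test a concrete case.** A transaminase rise on study drug with compatible timing occurs in a patient who entered on a statin (inclusion criterion 2). The protocol itself names statins as a possible cause of such rises (1.4). If the investigator regards the statin as a possible cause of this rise, the event falls in the undefined consistent-and-present cell.

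**Step 5: size.** A genuine reaction necessarily has consistent timing. Let q be the share of genuine reactions with another identifiable cause. The share that literally cannot be Yes is then q: 10% if q = 10%, 50% if q = 50%, 90% if q = 90%. The documents give no q, so the range is 0 to 100%.

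**Step 6: trace where the rating is used.**

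| Output | Uses the rating? |
|---|---|
| Related-TEAE and related-SAE tables, death listing (SAP 4.8.1) | Yes |
| SAEs after the 28-day window (protocol 10.3.1) | Yes |
| SUSARs (protocol 10.3.1, 10.3.3) | Only if the decision relies on the investigator's answer; no separate sponsor assessment is described |
| SAEs within the window (protocol 10.3.1) | No |
| All TEAEs (protocol 12.2.5) | No |
| Bleeding, glucose control, hepatic indicators (SAP 4.8.3) | No |
| Drug-induced liver injury (SAP Addendum section 9) | No; laboratory values |

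**The case against.** The best defence is that the definitions guide judgment and are not meant as an algorithm. Being on a statin does not make the statin the identified cause of a given event. Patients must have been on a stable dose for at least 4 weeks before the qualifying lipid measurements, and ALT or AST above three times the upper limit at Visit 1 is an exclusion, so attributing a later rise is a matter of judgment. Protocol 11.1 provides for interruption and re-challenge as a way to settle causation. The Yes label and the SAP both show that possibly related was meant to count. SAP 4.3.2 and 4.8.1 count a missing relationship as related in tables. Ratings are made blind, so nothing points to bias between arms.

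Much of this stands, and it limits the consequence. It does not remove the contradiction. The rule for missing ratings helps only if the field is left blank, whereas the protocol asks for Yes or No. Clear intent in the label does not help a site that applies the definition printed beside it.

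A reader might go further and infer that, with every patient entering on a statin, most genuine reactions, or essentially all liver events, can never be rated Yes. The documents do not support that. *Most* needs q above 50%, and no q is given. The AMR101 reactions listed in protocol 1.3 are arthralgia (3/309 = 1.0% on placebo, 14/622 = 2.3% on AMR101) and oropharyngeal pain; for ethyl-EPA in the large Japanese study it lists gastrointestinal and skin events. Protocol 1.4 attributes none of these to statins. Nor does the text force a No, since these events fail that definition as well. Extending the argument to bleeding would need the rate of antithrombotic use, which is not stated. Extending it to glucose would need diabetes medication to be a cause of worsening, which the documents do not say.

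**Conclusion.** The causality rule is wrong as written: it leaves two of four combinations without a category, and its Yes definition conflicts with its own label and with SAP 4.8.1. The expected effect is inconsistent rating or under-attribution of events with a competing explanation, transaminase rises on a statin being the clearest example. How many events are affected cannot be derived from the documents.

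A reader might also infer that the trial's safety comparison is compromised. It is not. The randomized comparisons of all TEAEs, events of special interest and liver injury do not depend on the rating, and SAEs within the 28-day window are reported whatever the rating. Because follow-up of patients off drug but still in the study is covered until 28 days after study completion, the related-only clause bears mainly on events after the study or after withdrawal from it. The severity is therefore below must-fix.

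The conclusion rests on reading each definition as a conjunction, as the text has it. It also assumes that the CRF completion guide, which is not among the documents, does not already supply different wording.

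**What to change.** In protocol 10.2, make the second category the complement of the first:

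- **Yes (related, probably or possibly related):** the time course is compatible and there is a reasonable possibility that study drug contributed, whether or not another cause is also possible.
- **No:** every other adverse event.

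Delete the condition in Yes that no other cause can be identified. Defining No as the remainder matters. A No that required another cause to explain the event fully would again leave out an event with compatible timing, no reasonable possibility of a drug contribution and no complete alternative explanation.

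Keep the list of further factors as guidance on whether the possibility is reasonable, and use the same wording in the CRF completion guide. SAP 4.8.1 needs no change, since it already counts possibly related as related.

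The cost is two sentences and a matching edit to the guide. The reported rate of related events may rise somewhat in both blinded arms. Sample size, alpha and endpoints are untouched.

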10.2.1. Serious Adverse Events

A serious adverse event (SAE) is defined as an AE that meets **any** of the following criteria:

- Results in death;
- Is life-threatening- Note: The term “life-threatening” in the definition of “serious” refers to an event in which the patient was at risk of death at the time of the event. It does not refer to an event, which hypothetically might have caused death, if it were more severe.
- Requires hospitalization or prolongation of existing hospitalization- Note: In general, hospitalization for treatment of a pre-existing condition(s) that did not worsen from baseline is not considered an AE(s) and should not be reported as a SAE(s).
- Results in disability/incapacity;
- Is a congenital anomaly/birth defect;
- Is an important medical event- Note: Important medical events that may not result in death, be life threatening, or require hospitalization may be considered an SAE when, based upon appropriate medical judgment, they may jeopardize the patient and may require medical or surgical intervention to prevent one of the outcomes listed above. Examples of such medical events include allergic bronchospasm requiring intensive treatment in an emergency room or at home, blood dyscrasias or convulsions that do not result in inpatient hospitalizations, or the development of drug dependency.

By design of this study SAEs that are endpoint events will only be recorded for the endpoint determination and not captured as SAEs. The intention is that the endpoint events are not reported to IRBs as SAEs, unless the IRB requires that these are reported. Investigators should specifically inform their institution/IRB of this plan and confirm whether or not they want the endpoint events reported. By agreement with the US FDA, these endpoints will also not be reported to the US FDA as SAEs; rather they will be reported as endpoint events. Following adjudication if the event is determined to not meet the criteria for an event, the event will be evaluated as an SAE beginning with that day as Day 0.

10.3. Serious Adverse Event Reporting – Procedure for Investigators

10.3.1. Initial Reports

All SAEs occurring from the time of informed consent until 28 days following the last administration of study medication (or until 28 days following study completion for ODIS patients) must be reported to the Sponsor or designee **within 24 hours** of the knowledge of the occurrence (this refers to any AE that meets any of the aforementioned serious criteria). SAEs that the investigator considers related to study medication occurring after the 28-day follow-up period will also be reported to the Sponsor or designee.

The investigator is required to submit SAE reports to the Institutional Review Board (IRB) or Independent Ethics Committee (IEC) in accordance with local requirements. All investigators involved in studies using the same investigational medicinal product (IMP) will receive any Suspected Unexpected Serious Adverse Reaction (SUSAR) reports for onward submission to their local IRB as required. All reports sent to investigators will be blinded.

In addition, regulatory agencies will be notified of SAEs per the requirements of the specific regulatory jurisdiction regulations and laws.

10.3.2. Follow-Up Reports

The investigator must continue to follow the patient until the SAE has subsided, or until the condition becomes chronic in nature, stabilizes (in the case of persistent impairment), or the patient dies. Within 24 hours of receipt of follow-up information, the investigator must update the SAE form electronically in the EDC system for the study and submit any supporting documentation (e.g., laboratory test reports, patient discharge summary, or autopsy reports) to the Sponsor or designee via fax or email.

10.3.3. Reporting by the Sponsor

IRBs and IECs will be informed of SUSARs according to local requirements. Cases will be unblinded for reporting purposes as required.

10.4. Exposure *in Utero* During Clinical Trials

If a patient becomes pregnant during the study, the investigator should report the pregnancy to the Sponsor or designee within 24 hours of being notified. The Sponsor or designee will then forward the Exposure *in Utero* form to the investigator for completion.

The patient should be followed by the investigator until completion of the pregnancy. If the pregnancy ends for any reason before the anticipated date, the investigator should notify the Sponsor or designee. At the completion of the pregnancy, the investigator will document the outcome of the pregnancy. If the outcome of the pregnancy meets the criteria for immediate classification as an SAE (i.e., postpartum complication, spontaneous abortion, stillbirth, neonatal death, or congenital anomaly), the investigator should follow the procedures for reporting an SAE.

